10.6.12.2 Rapid Test for Influenza Illness

The Microbiology Laboratory of the HIRRC will be supplied with rapid diagnostic tests capable of distinguishing influenza A from B (e.g., Remel Xpect[®] Flu A&B, Quidel QuickVue[®] Influenza A+B, Becton Dickinson DirectigenTM Flu A+B, or equivalent). Nasopharyngeal and/or oropharyngeal specimens will be collected from participants with Influenza-like Illness (section 10.6.9) using swabs, collection kits, and instructions provided or indicated by the test involved. Participants who develop influenza-like illness multiple times during the study period may be tested multiple times as well. Specimens will be promptly assayed according to the manufacturer's instructions.

10.6.12.3 Influenza Virus Culture

The Microbiology Laboratory of the HIRRC will be supplied with virus culture collection and transport tubes with Hank's medium (e.g., BD CellmaticsTM Viral Transport Pack, Remel MicroTestTM M4[®], or equivalent). These contain swabs with Dacron[®] tips and aluminum or plastic shafts to avoid damage to viruses present from calcium alginate or cotton tips and wooden shafts. Nasal and throat samples will be combined and stored at -70°C until it is determined by positive findings for influenza A to ship them to a specialist virology laboratory for culture and serotyping. The laboratory to perform such cultures will be determined by competitive tender by WHO among qualified reference laboratories.

10.6.13 Termination Visit

The final study visit will occur at ~ 56 days after dose 1 of **INF** vaccine, which should be approximately 28 days after dose 2. At this time, the 3^{rd} blood draw and a 3^{rd} ("insurance") dose of **INF** will be administered. If the participant does not return as scheduled for this visit, followup will be performed by home visit by study personnel.

10.7 Data Quality Assurance

10.7.1 Clinical Procedures

Personnel of CDC will visit the study site prior to initiation of the study to review with the site personnel information about the investigational agent, protocol requirements, randomization procedures, case report forms (CRFs), monitoring requirements, needle-free injection techniques, and reporting of serious adverse events.

HIRRC/CDC Needle-free Intradermal	Page 99	File: 4785-ID-INF-Prot-Engl-2008Jun24.doc
Influenza Study - CDC-ISO-4785	of 138	2008-Jun-24

10.7.2 Good Clinical Practices Monitoring

At visits during and after the study, the site will be monitored by CDC for compliance with current good clinical practices (cGCP) and other requirements, including accurate and complete recording of data on CRFs, source documents, and drug accountability records.

10.7.3 Data Handling

Case report form data will be entered in duplicate at CDC, using EPI-INFO (CDC, Atlanta, GA), Microsoft Access[®] (Redmond, WA), and/or equivalent software. Analysis will be performed by EPI-INFO, SASTM (SAS Institute, Cary, NC), or equivalent software. Analyses will be performed by a predefined analysis plan.

10.8 Statistical Methods and Determination of Sample Size

10.8.1 Statistical and Analytical Plans

10.8.1.1 Primary Efficacy Analysis

The primary analysis of efficacy will be comparison of the proportion of participants within each investigational route of administration – ID-JI-0.1 and IM-NS-0.1 – achieving seroconversion one month after the second dose of vaccine to each vaccine strain versus the control needle-syringe full-dose route (IM-NS-0.25). As defined in section 10.5.1.2, the criteria for *seroconversion* to a vaccine strain will be a hemagglutination inhibition (HI) assay titer of 1:40 or greater for those with initial undetectable titers, or an increase of 4-fold or greater from a measurable initial titer to final titer.

Each reduced-dose investigational study arm, ID-JI-0.1 and IM-NS-0.1, will be considered an acceptable alternative method of vaccination if there is no more than a twelve percent decrement in the proportion of participants seroconverting compared to that of the full-dose, IM, needle-syringe control vaccination comparator (IM-NS-0.25) (*non-inferiority* model).^{FDA1998, Chow2002}

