- Investigator-observed local injection site and systemic symptoms at 0 and 30-60 minutes, plus 2, 7, and 28 days after both the injections. Home telephone calls and home visits, if needed, by study staff on days 3, 9, and 29 for participants failing to return to clinic as scheduled.
- Prompted daily measurement and recording on parental diary form for 8 days following both study injections of local (tenderness, erythema, induration, ecchymosis, circumference) and systemic reactions (fever, anti-fever medication, loss of appetite, sleepiness, irritability, unusual or inconsolable crying, vomiting, diarrhea, convulsions, other to be specified).
- Unprompted reports on parental diary form or by telephone of these or other adverse events or symptoms occurring up to 28 days after each injection, plus report upon return for "bonus" booster vaccination 6 months after dose 2 + 28 days.

Statistical power considerations (§10.8):

For each of three treatment arms in the combined phases I and II, 150 participants will be studied, resulting in a total sample size of 450. This number results from rounding up, in anticipation of modest loss-to-followup, from a calculated 142 participants required per arm.

The sample size calculation is based on a *non-inferiority* model using an expected seroconversion rate of 86.4% derived from a mean from four prior clinical studies of Vaxigrip[®] in the similar age of range of 6 to 36 months. A twelve percent decrement, i.e., 0.104, is selected, corresponding to an *acceptable* seroconversion rate as low as 76.0% in the investigational study arms to demonstrate they are not worse than the control arm by more than this amount. Sample size parameters are $\alpha = 0.05$, *Power* = 0.80 ($\beta = 0.2$).

4. Table of Contents

1.	Title Page	1
2.	Signatures	2
3.	Synopsis	3
4.	Table of Contents	
5.	Study and Events Timeline	
6.	List of Abbreviations and Definition of Terms	
7.		
1.	7.1 Institutional Review Boards or Independent Ethics Committees	

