HIRRC/CDC Needle-free Intradermal	Page 48	File: 4785-ID-INF-Prot-Engl-2008Jun24.doc
Influenza Study - CDC-ISO-4785	of 138	2008-Jun-24

subjects >60 years at least one of seroconversion or significant increase in antihemagglutinin antibody titre in >30%, mean GMT increase >2.0, proportion of subjects achieving HI titre >60%.)^{CPMP1997} Elderly subjects generally respond less well to influenza vaccines than young healthy adults, and those with chronic debilitating medical conditions generally respond less well than healthy subjects of similar age.^{Fukuda2004}

"The results in children met the criteria defined for young adults; no criteria for children have been set."

Gonzalez, *et al*, studied two 0.25 mL doses of Vaxigrip® administered one month apart to 67 children from 6 months to 3 years (36 months) of age in an uncontrolled study. ^{Gonzalez2000} Seroconversion (see definition in section 10.5.1.2) was achieved by 83.7% of the children to the A/H3N2 strain, by 81.6% to the A/H1N1 strain, and by 61.2% to the B strain. Seroprotection (see definition in section 10.5.1.3) rates were 91.8%, 81.6%, and 93.9%, respectively. The geometric mean increases (section 10.5.1.3) were 9.8, 13.3, and 4.1, respectively.

In a recent unpublished poster presentation, ^{Saliou2005} manufacturer representatives summarized the data from manufacturer trials designated GRT04, GRT11 and GRT51 among children from 6 months to 3 years of age. Precise seroconversion and seroprotection rates were estimated from histogram bars without value labels by interpolating from the scale. The mean seroconversion rates were estimated at 84% for A/H3N2, 88% for A/H1N1, and 54% for B.

Among a pediatric population older than the one to be studied here, Lina, *et al* reported a study of 42 children from 8 to 10 years of age, finding seroconversion rates of 57% (A/H3N2), 76% (A/H1N1), and 29% (B) three weeks after a single 0.5 mL dose of Vaxigrip. ^{Lina2000} Seroprotection was 83%, 93%, and 100%, respectively. The geometric mean increase was 6.4, 10.1, and 2.3, respectively.

Averaging the 2-dose seroconversion rates in age groups of 6-36 months, similar to those to be studied here (6-23+ months), from the Gonzalez *et al* study and the three studies reported by Saliou *et al*, the mean SC was 85.2% (A/H3N2), 86.4% (A/H1N1), and 56.0% (B).

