10.8.1.2 Secondary Efficacy Analyses

Secondary efficacy analyses will compare the three study arms on the following:

- a. proportion seroconverting one month after the first dose of vaccine, but before the second dose
- b. proportions achieving seroprotection one month after both the first and second doses of vaccine. *Seroprotection* is defined as HI titers of ≥1:40, including among those pre-immune participants with detectable titers before vaccination.

HIRRC/CDC Needle-free Intradermal	Page 100	File: 4785-ID-INF-Prot-Engl-2008Jun24.doc
Influenza Study - CDC-ISO-4785	of 138	2008-Jun-24

- c. geometric mean titers (GMTs) of HI assays performed one month after both doses 1 and 2.
- d. satisfying the clinical criteria of the European guidelines for annual vaccine registration for adults aged 18 to 60 (there are none for children), ^{CPMP1997} that antibody responses to at least one strain of the vaccine achieve:
 - >40% seroconversion among participants
 - >2.5 increase in inverse geometric mean titer from pre-vaccination to final titers (e.g., from inverse GMT of 8 initially to final of ≥20)
 - >70% seroprotection among participants
- e. proportion with prompted and unsolicited adverse events following immunization.

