and clarify the issue, the reduced-dose IM arm is included in this trial with the same statistical assumptions as per the ID arm.

Applying a *non-inferiority* model using a score test for two independent proportions, ^{Farrington1990} a margin around these expected seroconversion rates (0.864) of twelve percent is selected, i.e., 0.104. This corresponds to an *acceptable* seroconversion rate as low as 0.760 (76.0%) in the investigational study arms, to demonstrate that the investigational arms are not worse than the control arm by more than this amount. (Decrements of up to 15% are suggested for non-inferiority trials in which the standard treatment rate is between 80% and 90%.^{Chow2003}) Model parameters were set at:

target
$$\alpha = 0.05$$

Power = $0.80 \ (\beta = 0.2)$

Standard group proportion (P2) = 0.864 (from prior studies) Actual experimental group proportion (P1.1) = 0.864 (anticipated) Equivalent experimental group proportion (P1.0) = 0.760 (lowest acceptable) Equivalent margin difference (D0) = -0.104 (acceptable twelve percent decrement) Actual margin difference (D1) = -0.104 (acceptable twelve percent decrement) Experimental group sample size (N1) = 142 Standard (control) group sample size (N2) = 142

The null hypothesis H_0 is that the seroconversion rate for the treatment arm is at least 12% lower than for the standard arm, and that under the alternative hypothesis H_a , the difference in seroconversion rates between the treatment and standard arms is less than 12% (i.e., the treatment is not inferior to standard). If the study rejects the null hypothesis H_0 and accepts the alternative H_a , we may conclude that the treatment is not inferior to standard, with only a 0.05 probability of reaching this conclusion due to random error.

Applying an alternative *superiority* model for two independent proportions (null case) using a one-sided Z test with pooled variance, ^{Chow2003} a sample size of 139 or greater in each group will detect with 80% power ($\beta = 0.2$) a superiority of ten percent or greater (seroconversion \geq 95%) for either of the investigational study arms over the control arm (assumed 86.4%). As for the non-inferiority model, above, the significance level of the test was targeted at $\alpha = 0.05$.

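### Stratifying the primary seroconversion comparison by day-0 serostatus is a free efficiency gain that the protocol does not take; its size cannot be fixed from the documents

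*Protocol*

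**What the plan says.** Protocol 10.8.1.1 defines the primary analysis: "The primary analysis of efficacy will be comparison of the proportion of participants within each investigational route of administration", for each vaccine strain, against the full-dose arm. Success means a decrement of no more than twelve percent. Section 10.8.2 sizes the comparison "using a score test for two independent proportions", with 0.864 in both arms, a margin of 0.104 and 142 evaluable children per arm.

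Section 10.5.1.2 gives seroconversion two rules. A child with a day-0 titre below 8 must reach 40. A child with detectable day-0 antibody must show at least a 4-fold rise. Serum is drawn from every child on day 0 (10.6.1, Table 5).

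Section 10.8.1.2(c) lists "geometric mean titers (GMTs) of HI assays performed one month after both doses 1 and 2" as a secondary comparison and mentions no baseline adjustment.

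For the one published study in children of 6 to 36 months, 10.4.2.4 gives seroconversion "by 81.6% to the A/H1N1 strain, and by 61.2% to the B strain". Seroprotection "rates were 91.8%, 81.6%, and 93.9%, respectively", in the order A/H3N2, A/H1N1, B. The four-study mean seroconversion for B is 56.0%. Section 10.7.3 refers to a predefined analysis plan, which is not at hand.

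**The concern.** Serostatus decides which event counts as seroconversion, so it may predict the outcome strongly. If it does, chance differences between arms in the share of seropositive children add variation to the non-inferiority difference, and a stratified estimate removes that part. The simple comparison leaves it in, although the covariate costs nothing: without the day-0 titre the endpoint cannot be calculated at all.

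B is the strain where this could matter most. It has by far the lowest expected seroconversion, and the protocol's source figures point to baseline antibody as a main reason.

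**Working it through.** **1. The plan's own figure.** Farrington-Manning score test, 0.864 in both arms, margin 0.104, power 0.80. Section 10.8.2 does not say whether this test is one- or two-sided ("with only a 0.05 probability of reaching this conclusion due to random error"). One-sided 0.05 is used here because it reproduces the stated size. The restricted estimates are 0.797 and 0.901.

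- s0 = √(0.797×0.203 + 0.901×0.099) = 0.501
- s1 = √(2×0.864×0.136) = 0.485
- n = [(1.645×0.501 + 0.842×0.485)/0.104]² ≈ 140.4, so 141 against the stated 142. One-sided 0.025 would need 179.

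**2. Unstratified power for B.** Rate 0.56 in both arms, n = 142, margin 0.104.

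- SE = √(2×0.56×0.44/142) = 0.0589
- Power = Φ(0.104/0.0589 − 1.645) = Φ(0.120) ≈ 0.548. The score version gives 0.551.

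**3. What the source study implies.** Under 10.5.1.2 a child below 8 on day 0 who ends at 40 or more has seroconverted. Anyone protected but not converted was therefore seropositive on day 0.

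- B: 93.9 − 61.2 = 32.7%, a lower bound on the share of seropositive non-converters.
- The five reported percentages fit only one denominator up to the 67 children enrolled: n = 49, with 46 protected and 30 converted. So at least 46 − 30 = 16 of the 49 − 30 = 19 non-converters (84%) were seropositive.
- A/H1N1: 81.6 − 81.6 = 0, so no such gap.

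**4. Gain from stratifying.** Let f be the seropositive share, s1 and s0 the seroconversion rates in seropositive and seronegative children, and p = f·s1 + (1−f)·s0 = 0.56. In large samples the variance of the stratified risk difference is the unstratified variance times (1 − R²), where R² = f(1−f)(s0−s1)²/[p(1−p)]. Power is then Φ(1.765/√(1−R²) − 1.645).

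The documents give neither f nor the stratum rates. The table assumes that seropositive non-converters are exactly 32.7% of all children, so s1 = 1 − 0.327/f.

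| f (assumed) | s1 | s0 | R² | Stratified power |
|---|---|---|---|---|
| 0.327 | 0.00 | 0.83 | 0.618 | 89% |
| 0.40 | 0.18 | 0.81 | 0.386 | 73% |
| 0.50 | 0.35 | 0.77 | 0.186 | 62% |
| 0.60 | 0.46 | 0.72 | 0.067 | 57% |
| 0.70 | 0.53 | 0.62 | 0.007 | 55% |
| 0.80 | 0.59 | 0.44 | 0.016 | 55% |

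Mixes slightly above the 32.7% bound behave alike: f = 0.60, 0.50 and 0.40 with s1 = 0.42, 0.30 and 0.10 give 59%, 67% and 85%. Simulating a Mantel-Haenszel-weighted risk difference agrees to within about a point. Reaching 80% needs R² of about 0.50.

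**5. Chance imbalance.** At f = 0.50 the SD of the between-arm difference in seropositive share is √(2×0.5×0.5/142) = 5.9 points. With s0 − s1 = 0.82 − 0.30 = 0.52, a one-SD imbalance moves the unstratified difference by 5.9×0.52 ≈ 3.1 points.

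**6. Type I error.** With a uniform 10.4-point decrement, the simulated one-sided error of the stratified test was about 0.05 in the mixes where this can be simulated. It cannot be in the mix with s1 = 0.10, because the decrement would push that rate below zero.

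**The case against.** - **An analysis plan could supply this.** Baseline stratification and analysis of covariance (ANCOVA) are ordinary SAP content, 10.7.3 points to such a plan, and 10.8.1.1 does not exclude adjustment. The score test is named only for sizing. This stands, and it is why the point is not an error or a contradiction. But 10.8.1.1 itself sets the primary comparison and its success rule, so a change of estimator is best fixed there before unblinding.
- **The simple comparison is not biased.** A reader might infer that serostatus imbalance corrupts the result. It does not: under randomisation it is ordinary sampling error, already in the standard error. The loss is of efficiency only.
- **The gain is not established.** A reader might infer that stratifying would lift B power by a definite amount, or to 80%. The stratum rates are not in the documents, and mixes that meet the same 32.7% bound give no gain. The bound itself is 16 of 49 in one uncontrolled study (exact 95% interval about 20 to 48%) of children up to 36 months, whereas this trial enrols below 24 months. The 56% is a mean over four studies, and for three of them no seroprotection rate is given.
- **Baseline is partly covered.** Mean geometric increase (10.5.1.3) uses day-0 titres, and seroprotection is analysed whatever the baseline. These show the pattern but do not sharpen the primary test.

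**Conclusion.** The point holds as an efficiency improvement. The primary comparison leaves unused a baseline value that the endpoint rule depends on and that every child supplies. The source figures make a gain for B plausible: unstratified power is about 55%, and stratified power could lie anywhere from about 55% to about 89%.

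This rests on B seroconversion of 56%, 142 evaluable children per arm, one-sided 0.05, the source study having used the protocol's definitions, and the assumed mixes in the table. It also carries the A/H1N1 margin of 0.104 over to B. Reading twelve percent as relative (0.12×0.56 = 0.067) makes unstratified power 31%, reading it as 12 points makes it 66%, and one-sided 0.025 with 0.104 makes it 42%.

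No gain is shown for A/H1N1, the strain the trial is sized on. The B shortfall comes from sizing on A/H1N1 while testing every strain, and stratification cannot be relied on to repair it.

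**What to change.** - **10.8.1.1:** prespecify for each strain a risk difference stratified by that strain's day-0 titre, below 8 versus 8 or more (Mantel-Haenszel weights or stratified Miettinen-Nurminen). Keep the same margin and error rate, and report the unstratified difference as supportive.
- **10.8.1.2(c):** compare log titres between arms by ANCOVA with log day-0 titre as covariate.
- **Cost:** wording only. No extra child, blood draw or assay is needed. The change should be dated before the allocation codes are released.

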10.8.2 Determination of Sample Size

The total participants of the combined phases I and II (N=450), results from 150 participants in each of three study arms. This number results from rounding up, in anticipation of an estimated 5% loss-to-followup, from a calculated 142 participants (*non-inferiority* model ^{FDA1998, Chow2002}) or 139 participants (*superiority* model) required per arm, derived using PASS 2002TM software (Number Cruncher Statistical Systems, Kaysville, UT, http://www.ncss.com),^{Hintze2005} as follows:

The full-dose, standard IM route control arm of the study (IM-NS-0.25) is assumed to achieve the mean seroconversion rate against the A/H1N1 strain (86.4%) demonstrated in 1 published ^{Gonzales2000} (76%) and 3 unpublished ^{Saliou2005} recent clinical trials (~88%, ~79%, ~97%) of Vaxigrip® influenza vaccine (Sanofi-Pasteur, Lyon, France) conducted among a similar age range (6-35 months) of children as those to be studied in this trial (6-24 months). (Immunogenicity for at least one strain satisfies European Committee for Proprietary Medicinal Product requirements for European registration. ^{CPMP1997}) This rate is somewhat lower but consistent with the 91% seroconversion reported after use of a different influenza vaccine, Fluzone®, manufactured by the same company at its Swiftwater, PA, USA plant. ^{SanofiPasteur2004, Hoberman2003}

Based on prior literature indicating equivalent serologic responses between standard, full-dose, needle-syringe influenza vaccination and (1) reduced-dose, needle-syringe intradermal (ID) vaccination (see section 9.4.2), as well as (2) reduced-dose jet injected (JI) ID vaccination (see section 9.4.4), the same 86.4% seroconversion rate is postulated for the investigational intradermal study arm.

There is a paucity of and some conflicting results among clinical trials of reduced-dose influenza vaccination comparing the same antigen dosage by the ID versus IM or SC routes (see section 9.4.3). Dose-sparing trials without an ID arm showed a small decrement in response, ^{Treanor2002} so reduced dosage via the standard IM route is suggested as a useful strategy in time of shortage. ^{Treanor2004} Others have called for careful clinical trials to confirm the effect of the ID route. ^{LaMontagne2004} To fulfill this call

HIRRC/CDC Needle-free Intradermal	Page 101	File: 4785-ID-INF-Prot-Engl-2008Jun24.doc
Influenza Study - CDC-ISO-4785	of 138	2008-Jun-24

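### Primary non-inferiority is tested for each strain, but the 80% power with 142 per arm holds for A/H1N1 only; for B it is 31–66%, depending on a margin the protocol does not fix

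*Protocol*

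**What the plan says.** **Primary comparison.** Section 10.8.1.1 compares each reduced-dose arm with the full-dose control on the proportion "achieving seroconversion one month after the second dose of vaccine to each vaccine strain versus the control needle-syringe full-dose route". An arm is an acceptable alternative "if there is no more than a twelve percent decrement in the proportion of participants seroconverting compared to that of the full-dose" control arm. That sentence names no strain and does not say whether the twelve percent is relative or in percentage points.

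**Sizing.** In Section 10.8.2 the control arm "is assumed to achieve the mean seroconversion rate against the A/H1N1 strain (86.4" percent). The same rate is assumed for both reduced-dose arms. With α = 0.05, power 0.80 and a score test, this gives 142 per arm, raised to 150 for 5% loss. The synopsis (statistical power considerations) sizes on an "expected seroconversion rate of 86.4% derived from a mean from four prior clinical studies of Vaxigrip" and names no strain.

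**Margin.** Section 10.8.2 expresses it in three ways:
- as a fraction of the expected rate: "a margin around these expected seroconversion rates (0.864) of twelve percent is selected, i.e., 0.104"
- as a fixed difference in the software inputs: "Equivalent margin difference (D0) = -0.104 (acceptable twelve percent decrement"
- in the alternative hypothesis, where "the difference in seroconversion rates between the treatment and standard arms is" below 12%

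**Expected rates.** Section 10.4.2.4 averages four two-dose trials in similar ages: "the mean SC was 85.2% (A/H3N2), 86.4% (A/H1N1), and 56.0% (B"). No power is given for A/H3N2 or B.

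**The concern.** The sizing and the primary analysis do not cover the same thing. Three strains are compared, and one is powered. The omitted strain that matters is B. Its expected rate of 56.0% has a binomial variance about 2.1 times that at 86.4%, so the same number of children gives a much less precise difference.

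The margin adds a second problem. At 86.4% the first two expressions coincide, because 12% of 0.864 is 0.104. At 56.0% all three separate, and the protocol does not say which one applies. The same B data could pass on one reading and fail on another.

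A reader of the synopsis would take 80% as the power of the whole primary endpoint. If B comes out inconclusive, that could be read as failure of dose sparing when the trial was never sized to settle B. If an arm must pass on every strain, its power cannot exceed the B figure.

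**Working it through.** **Inputs.** Rates 0.864 (A/H1N1), 0.852 (A/H3N2) and 0.560 (B) from Section 10.4.2.4. The score test, α = 0.05, equal true rates in the two arms, D = 0.104 and n = 142 per arm come from Section 10.8.2. Sidedness is not stated for the non-inferiority model; one-sided 0.05 is taken because it reproduces the sample size.

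**Formulas** (Farrington–Manning score test, equal arms, true difference 0, margin D):
- V1 = 2p(1 − p)
- V0 = p̃₁(1 − p̃₁) + p̃₂(1 − p̃₂), where p̃₁ and p̃₂ are the maximum-likelihood rates restricted to p̃₁ = p̃₂ − D
- n = [(1.645√V0 + 0.842√V1) / D]²
- power = Φ[(D√n − 1.645√V0) / √V1]

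**The plan's own figure.** For p = 0.864 and D = 0.104, the restricted rates are 0.797 and 0.901, so √V0 = 0.501 and √V1 = 0.485.
- n = [(0.824 + 0.408) / 0.104]² = 140.4. With the unrounded D = 0.12 × 0.864 = 0.10368, n = 141.2, which rounds up to 142.
- Power at 142 = Φ[(1.239 − 0.824) / 0.485] = Φ(0.856) = 80.4%.
- One-sided 0.025 would need 179 per arm and would give 70% at 142, so it is not the level used.

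**Variance ratio, B to A/H1N1.** (0.56 × 0.44) / (0.864 × 0.136) = 0.2464 / 0.1175 = 2.10.

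**B at 142 per arm** (√V1 = √(2 × 0.56 × 0.44) = 0.702; √142 = 11.916):
- Relative, D = 0.12 × 0.56 = 0.0672, √V0 = 0.7005: Φ[(0.801 − 1.152) / 0.702] = Φ(−0.50) = 30.8%
- Fixed, D = 0.104, √V0 = 0.698: Φ[(1.239 − 1.149) / 0.702] = Φ(0.13) = 55.1%
- 12 points, D = 0.12, √V0 = 0.697: Φ[(1.430 − 1.147) / 0.702] = Φ(0.40) = 65.7%

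**All strains, power at 142 per arm**

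| Strain (rate) | Twelve percent relative | 0.104 fixed | 12 points |
|---|---|---|---|
| A/H1N1 (86.4%) | 80% | 80% | 89% |
| A/H3N2 (85.2%) | 77% | 78% | 87% |
| B (56.0%) | 31% | 55% | 66% |
| Lowest acceptable B rate | 49.3% | 45.6% | 44.0% |

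**Robustness for B.**
- Exact binomial power at 142: 30%, 56% and 66%.
- All 150 per arm evaluable: 32%, 57% and 68%.
- The component B rates in Section 10.4.2.4 (54% and 61.2%) in place of 56.0%: 29–67% at 142 per arm, and up to 69% at 150.

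**The case against.** The strongest reply is that this is a disclosed choice. Section 10.8.2 names A/H1N1 openly and remarks that meeting criteria for at least one strain satisfies European registration requirements, and nowhere is 80% claimed for B. That explains the choice but does not remove the mismatch. The one-strain criterion enters the plan only as a secondary analysis (Section 10.8.1.2, item d), it is not the non-inferiority rule, and the primary analysis says each strain. The synopsis omits the strain altogether.

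A second reply is that 0.104 is the only margin written as a number, so 55% is the fair figure. It is a reasonable central reading, but the relative derivation and the 12% hypotheses stand beside it, and B falls short on all three.

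Third, Section 9.6.4 describes the primary endpoint as a titer of at least 40. On that endpoint the one B rate given (93.9%, Section 10.4.2.4) yields about 96% power or more at 142 per arm. But the synopsis, Section 10.5.1.2 and Section 10.8.1.1 all make seroconversion primary.

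Fourth, three of the four trial results behind 56.0% were read off unlabeled histogram bars. This limits precision, but the component rates lead to the same conclusion. For A/H3N2, the components quoted average (83.7 + 3 × 84) / 4 = 83.9%, which lowers its power slightly, to 74%, 76% and 86%.

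Finally, the choice of deciding strains may sit in the predefined analysis plan cited in Section 10.7.3. If so, a cross-reference answers that part. The power statement and the margin are fixed in the protocol itself.

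**Conclusion.** The concern holds. The stated 80% describes A/H1N1 and, approximately, A/H3N2. It does not describe B, one of the three primary comparisons, where power at 142 per arm is 31%, 55% or 66% depending on the margin reading. With no true difference, B would fail to show non-inferiority 34–69% of the time. This assumes a one-sided 0.05 score test, equal true rates and an expected B rate near 56%; no variation checked brings B to 80%.

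The consequence is limited to an inconclusive B result and its interpretation. Estimates, the A/H1N1 error rate and the 142 itself are unaffected. It should be corrected, because the power statement and the primary analysis do not match as written.

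**What to change.** 1. In the synopsis and Section 10.8.2, state that the 80% power applies to A/H1N1 at 86.4%. Fix the margin scale for B (relative, 0.104 or 12 points) and state B's power at that margin.
2. In Section 10.8.1.1, name before unblinding the strain result or results that decide whether an arm is acceptable, or refer to the predefined analysis plan if it already names them. Two workable forms are: A/H1N1 confirmatory, with A/H3N2 and B reported as differences with confidence intervals; or all strains required, with power stated as no higher than that for B.

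No extra participants are needed, and the change is to protocol wording. The price is that B's power is then visibly below 80%. If the second item alters the primary analysis enough to affect the study objectives, Section 10.13 requires DSMB notification and approval by both IRBs.
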